6.3.1.2 Secondary Objectives

The secondary objectives of this study are to evaluate: clinical symptoms including blood in stool, stool frequency, GER, feeding difficulties, sleep disturbance and poor growth

6.3.1.2.1 Blood in stool Blood in stool will be assessed by daily hemoccult stool test on Days 0, 1-14, 21 (+/- 1 day), 28 (+/- 1 day)

6.3.1.2.2 Stooling Infant stooling will be assessed by daily log capturing frequency, consistency, night stooling, and presence of mucus or gross blood

6.3.1.2.3 Infant GER Infant GER will be assessed by standard Reflux Questionnaire on Day 7, 14, 21, and 28

6.3.1.2.4 Infant Sleep Infant sleep duration/quality will be assessed by Questionnaire on Day 7, 14, 21, and 28

6.3.1.2.5 Infant Feeding Infant feeding difficulties will be assessed by Questionnaire on Day 7, 14, 21, and 28

6.3.1.2.6 Infant Growth Infant growth will be monitored at weekly visits by measuring weight, length, and head circumference

6.3.1.2.7 Adverse Events Supplement-related adverse events will be recorded by parents in a health log, in consultation with the study team and PI.

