6.3.2.1 Stool Sample Collection

In addition to being used for hemoccult testing, infant stool specimens will be analyzed as an exploratory objective of the study and will be collected once during the Baseline period and daily (when available) for Days 1-14, 21, and 28, and assessments may include the following markers:

- Fecal calprotectin levels
- Fecal pH levels
- Fecal metabolomics
- Markers of inflammation and enteric cytokines including, but not limited to, IL-1, IL-8 and TNF-alpha
- Levels of eosinophil-related granular proteins
- Intestinal permeability/integrity markers including, but not limited to, lipocalin (NGAL)

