9. STATISTICAL ANALYSIS

9.1 SAMPLE SIZE CALCULATIONS AND STATISTICAL ANALYSIS PLAN

9.1.1 Determination of Sample Size

Approximately 100 infants and 100 mothers will be recruited and screened for the study to obtain a sample size of 50 participants for randomization, assuming a 50 percent screen fail rate. Forty (40) participants are expected to complete the study assuming a 20 percent drop-out rate. This sample size is based on a literature review of randomized clinical trials and the anticipated changes to the microbiome based on previous studies of *B. infantis*.

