9.2.2 Study Participant Populations

Randomization Approximately fifty (50) infants will be randomized in a 1:1 ratio to treatment probiotic or placebo. Randomization will occur immediately after all baseline period tasks have been confirmed to be completed and provide acceptable data.

Populations for Analyses The modified Intent to Treat (mITT) population will include all infants who are randomized and receive at least one supplementation. The Per Protocol (PP) population will include all randomized participants who do not have major protocol deviations. Major protocol deviations will be defined prior to unblinding of the data. Analysis on primary and secondary objectives will be completed based on the mITT population and the PP population; analysis on the exploratory objectives (perception of treatment) will be completed based on the mITT population.

Descriptive Statistics Descriptive statistics (mean, median, and standard deviation, minimum and maximum) of the quantitative variables will be summarized using number of subjects (n). The qualitative variables will be summarized using counts and percentages. All summaries will be presented by treatment group and time point (where relevant).

All CRF and laboratory data will be analyzed. Comparisons between treatment groups will be performed using Fisher's exact test or Pearson's Chi-Square test for categorical data and one-way ANOVA with Tukey's post hoc comparisons for individual timepoints or two-way repeated measures ANOVA for all timepoints for continuous data. Mean and standard deviations for certain groups and timepoints will be used as estimates in power calculations for future studies. Missing data will not be imputed in this study.

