9.2.3 Efficacy Analysis

Primary Endpoint(s) The primary objective of the study is to assess the effectiveness of the probiotic, *B. infantis* INF108F, on modulating the gut microbiome composition of breastfed infants diagnosed with FPIAP from Baseline to Day 28, including colonization of INF108F. This will be measured using stool 16S analysis and quantitative PCR. Treatments will be compared using a Wilcoxon Rank Sum test.

Secondary Endpoint(s) The secondary objectives of this study as measured:

- Evaluating the reduction in stool frequency and improvement of stool consistency by Day 7 using Questionnaire
- Evaluating the improvement of infant GER symptoms by Day 14 using Questionnaire. Reduction by 50 percent from Baseline to Day 14 Infants with a reduction in the number of crying/fussing episodes of greater than or equal to 50 percent on Day 14 will be counted as a success. The number of successes per treatment group will be compared using a Chi-square or Fisher's Exact test, as appropriate.
- Evaluating the improvement of feeding difficulties by Day 14, using Questionnaire. The number of successes per treatment group will be compared using a Chi-square or Fisher's Exact test, as appropriate.

- Evaluating the improvement of infant's sleep by Day 14, using Questionnaire.
- Changes of stool cytokine profile by Day 28. The changes from baseline to Day 28 will be compared for the two groups using a repeated measures ANOVA.

Safety Analysis Fisher's Exact Test will also be used to compare treatment groups for SAEs and AEs resulting in withholding or discontinuing the study products. Adverse events will be summarized. Frequencies and percentages of subjects with treatment-emergent adverse events (TEAEs), serious TEAEs and TEAEs causing premature discontinuation will be provided by treatment group. An AE is treatment emergent if it 1) occurs after the first dose of randomized study treatment or 2) if it is present prior to receipt of randomized study treatment but worsens in severity or increases in frequency after the first dose of randomized study treatment.

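### The repeated measures ANOVA for continuous outcomes names no tested term, timepoints or sphericity correction; over many daily points its uncorrected treatment-by-time test can exceed its nominal level, and a baseline-adjusted target-day contrast is better

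*Combined protocol and SAP*

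**What the plan says.** Section 9.2.2 sets the general rule for comparing arms on continuous data. It offers two routes joined by an unqualified 'or': "one-way ANOVA with Tukey's post hoc comparisons for individual timepoints", or "two-way repeated measures ANOVA for all timepoints for continuous data". No rule chooses between them. The section does not say whether the treatment main effect or the treatment-by-time interaction is the test. It gives no covariance structure, sphericity correction or significance level.

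Section 9.2.3 uses a repeated measures ANOVA by name once, for stool cytokines: "The changes from baseline to Day 28 will be compared for the two groups using a repeated measures ANOVA". It does not list the timepoints to be entered. The same section targets Day 7 for stool frequency and names no test for it, so the general rule of 9.2.2 applies. For the primary endpoint it says "Treatments will be compared using a Wilcoxon Rank Sum test".

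The number of available timepoints depends on which section is read:

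- Section 6.3.2.1, stool specimens: "will be collected once during the Baseline period and daily (when available) for Days 1-14, 21, and 28", which is 17 points.
- Section 6.6.3, stool samples: baseline and Days 3, 14 and 28, which is 4 points.
- Section 6.4, Table 1: no stool collection on Days 8-13. Read as Days 0-7, 14 and 28, this is 10 points.
- Section 6.3.1.2.2, stooling: "Infant stooling will be assessed by daily log capturing frequency, consistency, night stooling, and presence of mucus or gross blood". This is 29 points if Days 0-28 are all used. Table 1 marks the log from Day 0 to Day 27, which is 28.

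**The concern.** The two treatment terms of this ANOVA answer different questions, and the plan does not say which one will be read.

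The treatment-by-time term is an omnibus test of whether the arms' profiles differ in shape on any day. Its F reference distribution is exact only under sphericity, meaning that differences between any two days are equally variable. This is an assumption of the test, not part of its null hypothesis, and equal correlation is one sufficient case. Stools one day apart are likely to be more alike than stools two or four weeks apart. With many daily points the assumption then fails, and the uncorrected test rejects more often than its nominal level.

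The treatment main effect averages over all days entered, including Day 0 before any product is given. It therefore estimates a diluted mean difference and not a change from baseline.

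The stake is the reading of the continuous secondary and exploratory outcomes, such as stool frequency, cytokines, calprotectin and pH. If the plan stays open, the analyst can choose after unblinding among tests that differ in error rate, in power and in the question answered.

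**Working it through.** **Inputs.** From the documents: "Approximately fifty (50) infants will be randomized in a 1:1 ratio to treatment probiotic or placebo" (9.2.2) and "Forty (40) participants are expected to complete the study assuming a 20 percent drop-out rate" (9.1.1). Assumed, because the documents give no value: nominal two-sided 5%, Gaussian complete data, the within-infant correlation and the effect size.

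**The plan's own figures.** 100 screened x 0.5 = 50 randomized; 50 x 0.8 = 40 completers, or 20 per arm. These agree. No power statement exists to reproduce.

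**1. Size of the uncorrected treatment-by-time test.** With k timepoints and n = 20 per arm, the test refers F to (k-1) and (k-1)(2n-2) degrees of freedom. For k = 17 these are 16 and 16 x 38 = 608. For each setting, 4,000 trials with no treatment effect were simulated (Monte Carlo standard error about 0.3-0.6 percentage points). In the serial model the correlation is r to the power of the number of days apart. In the mixed model the variance is split into a stable infant part (0.3-0.5), a serial part (0.2-0.3, r = 0.7-0.9) and measurement noise (the rest).

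| Timepoints entered | Serial, r = 0.5 to 0.95 | Infant + serial + noise |
|---|---|---|
| 29 (daily log, Days 0-28) | 9.4% to 18.8% | about 6-9% |
| 17 (Days 0-14, 21, 28) | 7.6% to 15.4% | 6.1-6.8% |
| 10 (Days 0-7, 14, 28) | 7.1% to 12.0% | 5.2-6.1% |
| 4 (Days 0, 3, 14, 28) | 4.8% to 7.5% | about 5% |
| 2 (Days 0, 28) | about 5% | about 5% |

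Under equal correlation between all days, the rate is about 5% on every schedule. The treatment main effect also stays at about 5%; its problem is dilution, not size.

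**2. Effect of a correction.** Greenhouse-Geisser multiplies both degrees of freedom by an estimate of epsilon. At 17 points and r = 0.9, mean epsilon is about 0.27, so 16 and 608 become about 4.3 and 164. In the serial settings at 17 points, Greenhouse-Geisser gives 3.4-5.2% and Huynh-Feldt 5.0-6.3%. Where noise dominates at 29 points, Greenhouse-Geisser is conservative (about 2-3%) and Huynh-Feldt gives 5.2-5.8%. The single contrast of Day 28 minus baseline stays at about 5% on every schedule.

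**3. Two timepoints only.** With just baseline and Day 28 entered, the interaction F equals the squared t statistic on change (1.3118 = 1.3118 in a worked case). Sphericity then holds by construction.

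**4. Power on two timepoints.** Assume SD 1, a shift of 0.9 SD at Day 28, and correlation rho between baseline and Day 28. The standard error is sqrt(2v/20), with v as below; power is from the t distribution on about 38 degrees of freedom.

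- Main effect: v = (1 + rho)/2, expected difference 0.9/2 = 0.45.
- Change: v = 2(1 - rho), expected difference 0.9.
- ANCOVA on the Day 0 value: v = 1 - rho², expected difference 0.9.

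| Test | rho = 0.5: SE, ratio, power | rho = 0.05: SE, ratio, power |
|---|---|---|
| Main effect | 0.274, 1.64, 36% | 0.229, 1.96, 48% |
| Change (interaction) | 0.316, 2.85, 79% | 0.436, 2.06, 52% |
| ANCOVA | 0.274, 3.29, 89% | 0.316, 2.85, 79% |

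Baseline adjustment is ahead of the change comparison at both correlations.

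**The case against.** The strongest reply is that the excess error is conditional. A reader might infer that the plan's test gives 10-18% false positives as a matter of fact. The documents do not support that. They state no correlation, do not say that a correction will be withheld, and state no 5% level. With measurement noise, which stool markers plausibly carry, the excess is small even with daily data. Section 6.6.3 would bring only four stool points, and sections 6.3.2.1 and 6.3.3.5 make the marker assays optional. All of this stands, so the rates are given here as a range tied to assumptions. The daily stooling log, however, does not depend on the conflict between the stool-sample schedules.

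A reader might also infer that neither treatment term can test the change from baseline to Day 28. That is wrong for cytokines if only those two days are entered: the interaction is then exactly the test of change. Section 9.2.3 speaks of comparing changes, so the interaction is its natural reading, and the main-effect power figures warn against one reading without describing a stated choice. What remains is that the plan lists neither the days nor the term.

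A third tempting step is to require a Day 28 contrast for every outcome. This would conflict with the plan's own targets: Day 7 for stool frequency and Day 14 for several symptoms in 9.2.3, and Days 7, 14 and 28 in 3.1.2.

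Finally, 9.2.2 does allow single-timepoint comparisons. That route avoids the sphericity problem, but nothing says when it applies, and it does not adjust for baseline.

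**Conclusion.** The point holds in a conditional form. The plan leaves the tested term, the timepoints and any sphericity correction open. If many daily points are entered without correction and serial correlation is strong, the treatment-by-time test runs at about two to nearly four times an assumed 5% level. If noise and stable infant differences dominate, or if only four points are entered, the excess is at most a few percentage points. With two points there is none, but the test of change still gives up power that baseline adjustment would recover: 10 percentage points at correlation 0.5 and 27 at 0.05, for an assumed 0.9 SD shift. The treatment main effect including Day 0 should not serve as the treatment test. The primary endpoint is not touched, so this is a change that should be made, not a flaw in the trial's main conclusion.

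**What to change.** Amend 9.2.2 and 9.2.3 before unblinding:

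- For each continuous secondary or exploratory outcome, name its target day and test the between-arm difference on that day by ANCOVA adjusted for the Day 0 value. Examples are Day 28 for cytokines and Day 7 for stool frequency. An equivalent choice is the same contrast from a mixed model on a few fixed days, with Day 0 as a covariate and unstructured covariance.
- State which days enter each analysis, after reconciling the stool schedules in 6.3.2.1, 6.6.3 and Table 1.
- If an all-timepoints ANOVA is kept as a profile analysis, report its treatment-by-time p-value with a Greenhouse-Geisser or Huynh-Feldt correction. State that the main effect including Day 0 is not the treatment test.

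No new data are needed. Section 5.4 already makes an acceptable baseline stool sample and baseline data a condition of randomization, so the covariate should be available. The costs are a short protocol amendment with IRB review under 9.4, a somewhat less sensitive profile test, and day-by-day detail that becomes descriptive.

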9.2.3 Efficacy Analysis

Primary Endpoint(s) The primary objective of the study is to assess the effectiveness of the probiotic, *B. infantis* INF108F, on modulating the gut microbiome composition of breastfed infants diagnosed with FPIAP from Baseline to Day 28, including colonization of INF108F. This will be measured using stool 16S analysis and quantitative PCR. Treatments will be compared using a Wilcoxon Rank Sum test.

Secondary Endpoint(s) The secondary objectives of this study as measured:

- Evaluating the reduction in stool frequency and improvement of stool consistency by Day 7 using Questionnaire
- Evaluating the improvement of infant GER symptoms by Day 14 using Questionnaire. Reduction by 50 percent from Baseline to Day 14 Infants with a reduction in the number of crying/fussing episodes of greater than or equal to 50 percent on Day 14 will be counted as a success. The number of successes per treatment group will be compared using a Chi-square or Fisher's Exact test, as appropriate.
- Evaluating the improvement of feeding difficulties by Day 14, using Questionnaire. The number of successes per treatment group will be compared using a Chi-square or Fisher's Exact test, as appropriate.

- Evaluating the improvement of infant's sleep by Day 14, using Questionnaire.
- Changes of stool cytokine profile by Day 28. The changes from baseline to Day 28 will be compared for the two groups using a repeated measures ANOVA.

Safety Analysis Fisher's Exact Test will also be used to compare treatment groups for SAEs and AEs resulting in withholding or discontinuing the study products. Adverse events will be summarized. Frequencies and percentages of subjects with treatment-emergent adverse events (TEAEs), serious TEAEs and TEAEs causing premature discontinuation will be provided by treatment group. An AE is treatment emergent if it 1) occurs after the first dose of randomized study treatment or 2) if it is present prior to receipt of randomized study treatment but worsens in severity or increases in frequency after the first dose of randomized study treatment.

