1. BACKGROUND AND SIGNIFICANCE

1.1 Background

Oral tolerance is one of the fundamental mechanisms in preventing food allergies in humans. Breaching of oral tolerance may potentially lead to the development of food allergies (FA). Allergic food reactions can be divided into 2 categories: immunoglobulin E (IgE)-mediated and non-IgE-mediated FA. The hallmark of IgE-mediated FA is the potential of life-threatening anaphylaxis. The frequency of IgE-mediated FA in US children is about 6-8%.

The non-IgE-mediated GI FA includes several clinical conditions, food protein-induced allergic proctocolitis (FPIAP), food protein induced enterocolitis syndrome (FPIES), eosinophilic esophagitis (EoE) and eosinophilic gastrointestinal disorder (EGID). FPIAP is likely the earliest manifestation of non-IgE-mediated FA in childhood, and perhaps the very first condition of breaching oral tolerance, as it occurs in early infancy (2 weeks to 2 months) (1). In a prospective birth cohort study (GMAP), we have demonstrated that a prevalence of 17% of infants with FPIAP typically present with mucusy bloody stools, GER, irritability and feeding intolerances (1), and have increased risk of developing IgE-mediated FA later in life (2). FPIAP is also a risk factor for developing EoE (3). Children with FPIAP often have eczema (1). These suggest a possible common mechanism in non-IgE-mediated and IgE-mediated conditions.

The human intestinal microbiome is found to play a key role in health and disease. Changes to the gut microbiota have been associated with a wide variety of diseases, including allergic diseases in human (4-9). It is known that the human gut microbiota undergoes rapid and dynamic changes during the first year of life (10-13). Many factors are known to influence the initial acquisition and subsequent composition of the gut microbiome in infants (11). These factors include mode of delivery, antibiotic exposure, presence of mother's milk and breastfeeding, social economic status and household living conditions (11). Additionally, prenatal factors and in-utero exposures to certain environments likely play a role in the acquisition and composition of the infant gut microbiota (11).

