1.4 Rationale for Selection of Investigational Product(s) / Intervention(s) and Regimen

B. infantis INF108F has been used in other trials and has been shown to be safe and well-tolerated in infants (term and preterm) when supplemented daily for variable durations. Studies of this strain in breastfed infants

demonstrate a significant change to the gut microbiome composition within days of initiating the supplement. This change generally persists beyond the supplementation period if infants continue to receive breast milk as all or part of their diet.

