4. SUBJECT SELECTION

4.1 Inclusion Criteria

Individuals who meet all of the following criteria are eligible for enrollment as study participants. Potential candidates will be identified at the Pediatrics at Newton Wellesley (PNW) and MGH Pediatric Gastroenterology Clinic. The recruitment will occur at Newton Wellesley Hospital or Massachusetts General Hospital.

- Infants, male or female, of all ethnic/racial groups, with a gestational period of 37 to 42 weeks
- Infants aged 1-90 days old with a documented FPIAP with either gross blood or microscopic blood in stools, without other possible causes
- Infants must be exclusively breastfed or at least half of oral intake is from breast feeding or from expressed breast milk
- A willing parent or legal guardian will sign the consent form either electronically or with a wet ink signature

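### The primary Wilcoxon test leaves out age at Day 0, which costs some precision, though not validity, at about 20 infants per arm

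*Combined protocol and SAP*

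**What the plan says.** Section 9.2.3 defines the primary objective as modulation of gut microbiome composition "from Baseline to Day 28, including colonization of INF108F", measured by 16S analysis and quantitative PCR. The whole of the stated method is "Treatments will be compared using a Wilcoxon Rank Sum test". No single summary variable, covariate or stratum is named. The general methods in 9.2.2 name none either, and 5.4 describes 1:1 allocation without stratification.

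On age, section 4.1 admits "Infants aged 1-90 days old with a documented FPIAP", and section 1.1 states: "It is known that the human gut microbiota undergoes rapid and dynamic changes during the first year of life". Section 9.2.4 lists age among the demographic data, for summary tables only.

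On feeding, section 4.1 states: "Infants must be exclusively breastfed or at least half of oral intake is from breast feeding or from expressed breast milk". Section 1.1 counts "presence of mother's milk and breastfeeding" among the factors that shape the infant microbiome. Section 1.4 says of the product's effect: "This change generally persists beyond the supplementation period if infants continue to receive breast milk as all or part of their diet".

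Section 9.1.1 expects 50 infants randomized and 40 completing. Section 9.2.2 says missing data will not be imputed.

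**The concern.** A newborn and a three-month-old can enter the same trial, and by the protocol's own account the microbiota is changing fast over that period. If the ranked outcome depends on age, that part of the between-infant spread is treated as noise. A chance difference in age between the arms also goes uncorrected in the one trial that will be run.

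With about 20 infants per arm, an avoidable loss of precision could matter for a moderate effect on overall composition. Age is known before randomization and collected anyway, so using it needs no new data.

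**Working it through.** **The plan's own figures.** 100 screened × (1 − 0.50) = 50 randomized; 50 × (1 − 0.20) = 40 completers, or 20 per arm. This reproduces 9.1.1 and the synopsis. No effect size, SD, alpha, sidedness or power is stated, so no power figure can be reproduced. Everything below uses assumed inputs.

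**Approximate gain.** Let R² be the share of outcome variance explained by the covariates (assumed). The detectable difference at 80% power, two-sided 5%, is (1.960 + 0.842) × √(2/20) × √(1 − R²) in SD units. The equivalent sample size per arm is 20/(1 − R²).

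| R² | Detectable difference | Equivalent n per arm |
|---|---|---|
| 0 | 0.89 SD | 20.0 |
| 0.1 | 0.84 SD | 22.2 |
| 0.2 | 0.79 SD | 25.0 |
| 0.3 | 0.74 SD | 28.6 |

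**Simulated power.** Assumptions: 20 per arm, ages even over 1-90 days, normal errors, two-sided 5%, true shift 0.8 SD. The adjusted test is Quade's: rank the outcome and the covariates, regress one on the other ignoring arm, and compare the residuals between arms. The range covers age alone and age plus feeding type (30% partly breastfed, assumed). With 4000 runs the Monte Carlo standard error is about √(0.67 × 0.33/4000) = 0.7 points.

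| R² | Wilcoxon | Quade |
|---|---|---|
| 0 | about 67% | 1-2 points lower |
| 0.1 | about 67% | 68-70% |
| 0.2 | about 67% | 74-75% |
| 0.3 | about 67% | 78-80% |

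Type I error for Quade's test was 4.8% to 5.7%. A separate check used ordinary regression on ranks, a 0.93 SD shift and half the infants partly breastfed. It gave 79% against 82%, 80% against 86% and 79% against 90% at R² of 0.1, 0.2 and 0.3. At R² = 0 it gave 80% against 78%.

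**Larger effects.** At 1.2 SD the gain is about 1-4 points (for example 96% against 98% at R² = 0.2). At 1.5 SD both tests have about 99% power or more. For a colonization-type outcome (10% of placebo and 60% of active infants colonized, covariates explaining 30% of the level among those colonized; all assumed), Wilcoxon gave 92.7% and Quade 92.0%, so there was no gain.

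**Chance imbalance in age, 25 per arm.** SE of the difference in mean age = SD × √(2/25).
- Ages even over 1-90 days: SD 25.98, SE 7.35, 10/7.35 = 1.36, so the probability of a gap of 10 days or more is about 17%.
- Ages even over 14-60 days, close to the 2 weeks to 2 months of onset given in 1.1: SD 13.3, SE 3.8, 10/3.76 = 2.66, so the probability is about 1%.

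Both age distributions are assumptions.

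**The case against.** The strongest reply is that this is a preference for efficiency and not an error. Under randomization the unadjusted test holds its type I error, and chance imbalance is already allowed for in that error rate. This stands. A reader might infer that the primary result would be biased or invalid, but nothing in the design supports that.

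A reader might also infer that the protocol names exclusive versus partial breastfeeding as a driver of the outcome. It does not. Section 1.1 lists the presence of breast milk, which every eligible infant has, and 1.4 treats breast milk as all or part of the diet alike. Nor does any section show exclusive versus partial feeding recorded as a variable: eligibility needs only the half-of-intake threshold, and the feeding log in 6.1.2 and 6.1.5 is described as recording study-product feeds. Feeding type is therefore a conditional covariate at most.

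Age is better supported, but not without limits. It is absent from the list of factors in 1.1. The supporting sentence concerns the whole first year and does not say how much varies within 90 days. If most infants present near the stated age of onset, age can explain less and a large imbalance is unlikely.

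The gain also shrinks where effects are large. The protocol gives reason to expect that for colonization: it says the organism is missing from most infants, excludes prior exposure, and reports change within days of starting. The gain shrinks too if change from baseline is ranked, since some age-related variation is then already removed. These points limit the size of the gain. They do not remove it for broader composition measures with moderate effects, which the primary endpoint also covers.

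**Conclusion.** The point holds as a modest and inexpensive gain in precision. The primary test ignores a baseline variable that is already collected, has a wide eligible range, and relates to an outcome the protocol describes as changing rapidly in early life.

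The main benefit is for a moderate effect. At 0.8 SD with 20 per arm it is roughly 1 to 13 points of power as the variance share goes from 10% to 30%, against a loss of about 1-2 points if the share is zero. Neither the effect size nor the variance share is in the documents, so these figures are illustrative. The case for acting is that the possible loss is small and the possible gain is several times larger. The documents do not support calling the planned test invalid, treating feeding type as an established covariate, or expecting a serious age imbalance.

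**What to change.** In 9.2.3, make the primary comparison Quade's rank analysis of covariance, applied to whichever value the Wilcoxon test would rank, with age at Day 0 in days as covariate. Add feeding type (exclusive versus partial breast milk) only if it is recorded at baseline. Report the unadjusted Wilcoxon test beside it.

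Fix this before any unblinded look, including the interim analysis in 9.3, which an unblinded statistician runs once at least 10 infants have completed. Section 9.4 requires a protocol amendment and IRB review for changes to the principal features of the analysis plan, so the change should go through that route.

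The cost is a short amendment and about 1-2 points of power if the covariates explain nothing. Age needs no new data. The value to be ranked must be named for either test to be carried out, because 9.2.3 does not yet specify one.
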